### **Design and Methods:**

#### **General overview:**

We propose a group comparison study (gain-framed intervention vs. unframed intervention, starter package of 2 weeks of nicotine patches and lozenges vs. no medication) to evaluation methods to boost rates of smoking cessation for a high-risk group of smokers (N=367) with varying levels of motivation across 3 study sites (MUSC, Ralph H. Johnson Veteran Administration and Yale). All eligible study participants will be randomized to receive either: 1) Unframed Messaging (hereafter referred to as UM) with no medication, or 2) Gain-framed Messaging + Meds (i.e., 1 gain-framed video and print materials + 2 week starter pack of NRT; hereafter referred to as GM+M).

**Participants:** Our target sample will be 367 lung screening patients who currently smoke at each of 3 study sites: MUSC), Ralph Johnson VA, and Yale Cancer Center); Total N=367. The following eligibility criteria will ensure that we obtain our study sample of lung screening patients. **Inclusion:** 1) 50 years or older (we see no reason for an upper limit given supportive evidence for cessation among elderly), 2) at least a 20 pack year history of smoking (i.e., the base population of high risk smokers to get screened) as assessed by the patients ordering healthcare provider or the research team, 3) current smoker (defined as any smoking in the past 30 days – this is the criteria our lung cancer screening programs will use to trigger tobacco treatment interventions), 4) willing to be randomized, 5) English speaking; **Exclusion:** 1) unstable psychiatric/medical conditions such as suicidal ideation, acute psychosis, severe alcohol dependence, or dementia, and 2) known allergy to adhesives, and 3) current participation in another tobacco treatment program (e.g., using medication from a primary care doctor, quitline, etc).

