
**Follow-up:** Participants will complete assessments at a 1, 3, and 6 month follow-up session. Research staff will meet the MUSC Charleston participant in a public location that is convenient to the participant or conduct the follow-up via phone call. MUSC Charleston patients will also have the option of coming in to the clinic at Hollings Cancer Center for the follow-up meeting. All participants recruited from MUSC Lancaster, MUSC Chester, MUSC Florence, and MUSC Columbia will complete all visits remotely. If the participant has an in-person meeting, we will complete a breath CO test and a battery of assessments. If patients elect to complete these visits via phone call and report that they continued to smoke, a CO breath test will not be obtained. However, if the patient reports having quit smoking during the phone call, the research staff will schedule a visit to obtain the CO breath test. CO will be collected using the Bedfont Smokerlyzer for in-person visits or the Bedfont iCO smokerlyzer for remote visits. If CO is obtained remotely, we will mail a breath CO monitor to the participants with instructions for use. At a prearranged time, participants will be sent a link to a HIPAA Compliant video platform. Participants will virtually meet with research staff and will complete the breath CO sample live so that we can be sure it was the participant who provided the sample and reduce the chance of sample falsification. The CO device will also email a report of the CO sample to research staff. We plan to pay participants \$10 for completion of the 1- and 3-month follow up visits and \$30 for the completion of the 6-month visit. If the study participant is not available to meet in person or by phone, we will mail the follow up questionnaire to them to fill out and return via mail to us. Additionally, we can also send patients a link to the questionnaires via REDCap and contact them over the phone to get their timeline followback.

**Safety protocol:** To ensure the safety of the research assistant they will adhere to the following safety guidelines:

- Confirm with participants by phone before the visit
- Send meeting information to the Study Coordinator prior to leaving for the meeting
- Meet in public buildings where you feel safe, and not in parking lots, or public parks

Send a message to the Study Coordinator to confirm that the meeting has ended and you are leaving the meeting location

Never meet a participant after dark

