### **Statistical Considerations**

#### **Power and Sample size:**

We propose to test the primary hypothesis that rates of smoking cessation will be significantly higher 6-months after lung screening for the smoking cessation strategy involving a gain-framed intervention + 2 weeks of nicotine patches and lozenges compared to a strategy of an unframed behavioral intervention + no medication. We assume a biologically confirmed 7-day point prevalence abstinence rate at the 6 month follow up visit of 10-13% for the participants randomized to receive no NRT or gain framed messaging based on USPHS guidelines (Table 6.7 and 6.8 of USPHS Guidelines). In studies with a similar 2 week NRT exposure, 6 month abstinence rates varied from 16-34 % and a conservative estimate of a 20% abstinence rate in those receiving NRT only will be assumed. Based on previous work we estimate that the abstinence rate of in those receiving both NRT and gain framed messaging will be 10-11% increased over those with unframed messaging. Based on these estimates, we will have 80% power with a type 1 error rate of 5% to detect the conservative difference of between those receiving gain framed messaging + NRT (28%) and those receiving unframed messaging and no NRT (13%) with 123 participants randomized to each of the 4 treatment groups (total n=492 Participants). This assumes that the two treatment sites are moderately correlated (ICC=0.85) and randomize equal numbers of patients to each treatment cell. Additionally, we anticipate that 15-20% of our participants will fail to report 6 month follow up outcome data (LTF, death, moved out of area), accounting for a 20% attrition during the study follow up, we would need to randomize **n=367 participants** across all sites (179 randomized at Yale and 179 between MUSC and the VA) to maintain adequate power to detect the clinically meaningful difference stated. Assuming an abstinence rate of 14-17% in the group receiving unframed messages, we will have >80% power with a type 1 error rate of 5% to detect an 11% increase in abstinence in those receiving gain framed messages with the sample size stated for aim 1. We considered but opted against powering our trial on the treatment interaction, as this would require >5,000 participants.

Anticipated abstinence rates – 6 months	Gain-framed Intervention	No Message Intervention	
2 week starter pack NRT	28-30%	18-20%	23-25%

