strategy involving a gain-framed intervention + 2 weeks of nicotine patches and lozenges compared to a strategy of an unframed behavioral intervention + no medication. Primary and secondary models will be developed including the effects of both randomized conditions; gain framed vs. unframed messaging and NRT vs. no medication, and a cluster effect of study site. Models will be computed both unadjusted and adjusted for significant covariates found in the preliminary analysis. For these efficacy analyses, 7-day point prevalence abstinence will be defined as having no cigarettes (or other tobacco products) for 7 days, confirmed by CO breath test less than or equal to 10 ppm. All randomized participants will be included in the analyses (intent-to-treat approach), and participants will be considered non-abstinent at any missed visit (drop-out/lost-to-follow-up included). To comprehensively analyze the longitudinal efficacy of gain framed messages and NRT sampling, the entire study time course will be analyzed with repeated measures logistic regression using a Generalized Estimating Equation framework. Continuous abstinence (CA) from the time of lung screening to the 1 and 3 month follow-ups (Weeks 4 and 12) and to final follow-up visit (Week 26) will be assessed using logistic regression analysis. Time to first lapse (puff) and time to relapse (first of 3 consecutive days smoking  $\geq 1$  cigarette) will be analyzed using Cox Proportional Hazard models with effects of both randomized conditions in a 2x2 design; gain framed vs. unframed messaging and NRT vs. no medication, and a cluster effect of study site. In addition to the primary intent-to-treat analyses, additional exploratory approaches (e.g., modified intent-to-treat models, per protocol analysis, and completer analysis) will be undertaken as indicated and a sensitivity analysis comparing these models to the ITT model will be completed.

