Adverse Events (AE) and Serious Adverse Events (SAE) will be recorded during the duration of the treatment period. All cause treatment emergent adverse event and serious adverse event frequencies will be compared through the use of analysis of variance models. Of particular interest will be (S)AEs that lead to treatment suspension or study discontinuation. Study retention will be assessed by two methods; total number of treatment visits attended will be compared using Poisson regression for count data, while the number of days retained will be assessed using Cox Proportional Hazards regression models.

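### Poisson regression for visits attended overstates the standard error, so a non-significant result cannot be read as balanced attendance (minor, supportive analysis)

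*Combined protocol and SAP*

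**What the plan says.** The last paragraph of Statistical Analysis assesses retention in two ways. First, "total number of treatment visits attended will be compared using Poisson regression for count data". Second, "while the number of days retained will be assessed using Cox Proportional Hazards regression models". No robust, scaled or quasi-Poisson variance is stated for the first, and the term treatment visits is not defined.

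The Follow-up paragraph under Study Interventions sets the schedule: "Participants will complete assessments at a 1, 3, and 6 month follow-up session". Power and Sample size gives the only attrition figure: "we anticipate that 15-20% of our participants will fail to report 6 month follow up outcome data".

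Two other statements in Statistical Analysis bear on the point. For the efficacy analyses, "participants will be considered non-abstinent at any missed visit". The plan also lists modified intent-to-treat, per-protocol and completer analyses, and says that "a sensitivity analysis comparing these models to the ITT model will be completed".

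**The concern.** A Poisson model takes the variance of a count to equal its mean. Visits attended cannot behave like that here. Most participants will attend two or three visits out of three, so the mean sits close to the ceiling and there is little room for spread. The model-based standard error is then too wide and the test rejects too rarely.

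Retention is a supportive analysis, but readers will look at it. Because a missed visit is scored as non-abstinent, they will want to know whether the arms were followed equally well. A large p-value from a test that can hardly reject would give unearned reassurance.

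**Working it through.** The documents give no variance, standard error or power for the retention analyses, so there is no stated figure to reproduce.

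**Inputs from the documents**
- Three follow-up visits, at months 1, 3 and 6 (Follow-up).
- 15-20% without month-6 data, so 80-85% attendance at month 6 (Power and Sample size).
- Two arms (General overview) and 367 participants in total, split 184 and 183 for the simulations.

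**Assumptions, not in the documents**
- Attendance at months 1 and 3, and the correlation ρ between one person's visits.
- A two-sided 5% test; the plan does not state sidedness.

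**Step 1. Standard error ratio.** Let μ be the mean number of visits attended and V its true variance. With equal arms of size n, the Poisson standard error of the log rate ratio is √(2/(nμ)) and the true one is √(2V/(nμ²)). The ratio is √(μ/V), and n cancels. With constant attendance p, μ = 3p and V = 3p(1−p)(1+2ρ).

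| p | ρ | μ | V | SE ratio |
|---|---|---|---|---|
| 0.80 | 0 | 2.40 | 0.480 | 2.24 |
| 0.80 | 0.3 | 2.40 | 0.768 | 1.77 |
| 0.80 | 0.7 | 2.40 | 1.152 | 1.44 |
| 0.80 | 1 | 2.40 | 1.440 | 1.29 |
| 0.85 | 0 | 2.55 | 0.383 | 2.58 |
| 0.85 | 0.3 | 2.55 | 0.612 | 2.04 |
| 0.85 | 0.7 | 2.55 | 0.918 | 1.67 |
| 0.85 | 1 | 2.55 | 1.148 | 1.49 |

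**Step 2. The direction does not depend on ρ.** A count between 0 and 3 has variance of at most μ(3−μ). At μ = 2.4 that is 2.4 × 0.6 = 1.44, against the Poisson value of 2.4. At μ = 2.55 it is 2.55 × 0.45 = 1.15, against 2.55. No attendance pattern with these means brings the ratio down to 1.

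**Step 3. Other attendance patterns.**
- Permanent dropout, with attendance declining to 80-85% at month 6: ratio 1.64 to 2.41 over the patterns tried.
- Declining attendance with independent misses (simulated): 2.75 to 3.18.
- Intake counted as a fourth visit that everyone attends, constant 80-85% afterwards: μ rises by 1 and V is unchanged, giving 1.54 to 3.05.

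**Step 4. Type I error.** If the standard error is too large by a factor k, the real two-sided error rate is about 2[1 − Φ(1.96k)]. This gives 1.1% at k = 1.29, 0.5% at k = 1.44 and 0.006% at k = 2.04. In simulations with attendance declining equally in both arms (4,000 runs per scenario), model-based Poisson rejected in 0.0% of trials and robust-variance Poisson in about 5%.

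**Step 5. Power to see a difference.** The splits below are illustrative.

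| Scenario | Poisson, model-based | Poisson, robust | Log-rank on days retained | Month-6 chi-square |
|---|---|---|---|---|
| Missing at month 6: 14% v 24%, attendance declining | 2-10% | 64-95% | 70-71% | about 70% |
| Attendance 85% v 75% at every visit | 42-44% | 67-99% | 68-70% | 67-68% |

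The ranges cover independent, correlated and permanent-dropout patterns. The log-rank test stands in for the Cox score test, with days retained taken to the last visit attended. How much power Poisson loses depends on the pattern; in every pattern tried it does worse than the other three.

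**The case against.** The strongest case on the other side has four parts.

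- **The Poisson test is not the only retention analysis.** The same sentence plans Cox regression on days retained, which has no dispersion problem and had about 70% power for a 10-point difference in month-6 loss, much the same as comparing month-6 loss directly. This stands. A reader might infer that the plan hides differential attrition or would falsely certify balance. The documents do not support that: the Cox analysis can detect dropout, completer and other sensitivity analyses are planned, and no decision or statement of balance is tied to the Poisson p-value.
- **The link to the primary endpoint is loose.** Only the month-6 visit feeds the primary time point. Misses at months 1 and 3 enter the longitudinal GEE but not the month-6 result, so total visits is a weak proxy whatever its variance. This stands, and it is why month-6 loss should be reported separately.
- **The size rests on assumptions.** The documents give neither the between-visit correlation nor attendance at months 1 and 3, and the cap of three is inferred from the follow-up schedule. This stands for the size. It does not touch the direction (step 2).
- **Naming Poisson regression does not rule out a robust variance.** True, but the plan does not state one, and the default model-based variance is the wrong one here.

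The Cox analysis does not make the visit count redundant. If days retained runs to the last contact, a participant who misses month 1 or month 3 and returns at month 6 counts as fully retained. Of the two methods, only the visit count registers such gaps.

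**Conclusion.** The point holds as a minor correction to a supportive analysis. As written, the Poisson comparison of visits attended has a standard error that is too large: about 1.3 to 2.6 times at constant 80-85% attendance across correlations from 1 to 0, and 1.4 to 2.0 times for correlations of 0.7 to 0.3. Other attendance patterns, or counting intake, can take it somewhat above 3. The real type I error is near zero in most settings and about 1% in the least unfavourable one. A non-significant result should therefore not be read as balanced attendance.

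The size rests on the assumed correlation and attendance pattern, and on model-based variance being used. The direction needs only the cap of three and a mean near 2.4 to 2.55.

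The conclusion goes no further. The Cox analysis of days retained is sound on this point and the primary test is unaffected. What remains uncovered is month-6 attendance by arm, which neither retention model isolates.

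**What to change.** In the retention paragraph of Statistical Analysis:

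1. Define which visits count (three follow-ups, or four visits with intake) and what counts as attended, since follow-up may be completed in person, by phone, by mail or through REDCap.
2. Replace the Poisson comparison with a logistic GEE on attendance at each visit, clustered on participant, or with a binomial model for visits attended out of the number scheduled, using robust variance. Keeping Poisson with robust variance would also do.
3. Report missing month-6 outcome data by arm as a risk difference with 95% CI. Because reported quits need CO confirmation, show separately those who completed the assessment without a usable CO result.
4. Keep the Cox analysis of days retained and state how days retained is measured.

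The cost is a few lines of SAP wording and one added table row. Attendance and CO results come from the follow-up already planned, so no new measurement is needed, and the sample size and primary test stay as they are.

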#### **Recruitment, Feasibility, and Timeline**

Patients eligible for this study come from our lung cancer screening programs at our 3 study sites (MUSC, VA and Yale). Because the smoking cessation treatment programs led by [name] and [name] are clinical services, we have access to any and all of these patients for recruitment and are able to easily identify them through the Epic Medical Record (which is used at both study sites). Moreover, because [name] is the Co-Director of the Lung Cancer Screening Program at MUSC and with the support of [name] (see attached

letter), who is the Director of the Lung Screening and Nodule Program at Yale, we have full access to all lung screening patients at those study sites. [name] is the director of the lung cancer screening program at the VA and will be able to assist us in identifying all eligible participants that come through the lung cancer screening program. Because the USPTF recently recommended lung cancer screening for high-risk individuals and CMS covered lung screening as a benefit, many insurers are now covering lung cancer screening for high-risk patients, so these numbers should continue to grow rapidly. At HCC, Between March 1, 2015 and September 1, 2015, we have had 50 patients screened under physician referral to the screening program (approximately 8 per month). We have engaged the primary care physicians at MUSC (University Internal Medicine) and are conducting outreach with these physicians to increase referrals for lung cancer screening at MUSC. [name] of the Lung Cancer Screening Program at MUSC, [name] (a co-investigator on this grant), conducted similar outreach activities this past year at the Charleston VA and was able to screen 400 patients in the first year the program was open. Thus, we anticipate that our number of patients we are able to recruit will grow rapidly in the coming year. At YCC, there are 100 patients scheduled for screening over the next 4 months. Given the start date of this grant project and the time needed to prepare for the trial after the grant is awarded, we are highly confident that we will easily be able to meet our recruitment goal of approximately 1 participants per month (7 patients per month per site, VA/MUSC and Yale). This seems quite feasible given the large (and quickly growing) pool of patients available. The study timeline is described below:

- Months 1–6: Create gain-framed intervention materials, obtain study medication, train staff on study procedures, and finalize IRB approval.
- Months 7–51: Actively recruit 367 participants (approximately 14/month) and follow for 6 months.
- Months 50–60: Complete follow-up interviews, data analyses, prepare presentations and publications.

#### **Strengths and Overall Impact**

The proposed research has numerous strengths including: a) an experienced multi-disciplinary team; b) a timely research question, namely how to optimally enhance smoking cessation in growing populations of current smokers who are receiving lung cancer screening; c) gain-framed smoking cessation messages specifically developed for lung screening patients; d) an innovative pharmacotherapy strategy for all smokers; and e) ability to easily translate our findings to the growing number of lung cancer screening programs across the country. The findings from this research will have high overall impact by filling gaps in our knowledge of tobacco cessation in this high-risk population of smokers. These findings and the sharing of materials developed as part of this research will assist cancer centers and other healthcare organizations to maximize management of lung cancer screening patients with proven interventions for cessation, to have the greatest possible impact on lung cancer incidence and mortality.

#### **PROTECTION OF HUMAN SUBJECTS**

##### **RISKS TO THE SUBJECTS**

##### **Human Subjects Involvement and Characteristics**

In this experiment, participants will be recruited to participate in a smoking cessation study in the context of lung cancer screening. For the randomized controlled study, we will use the following inclusion and exclusion criteria. Inclusion: 1) 50 years or older (we see no reason for upper limit given supportive evidence for cessation among elderly), 2) 20 pack year history of smoking (i.e., the base population of high risk smokers to get screened), 3) current smoker (defined as any smoking in the past 30 days – this is the criteria our lung cancer screening programs will use to trigger tobacco treatment interventions), 4) willing to be randomized, 5) English speaking; Exclusion: 1) unstable psychiatric/medical conditions such as suicidal ideation, acute psychosis, severe alcohol dependence, or dementia, and 2) contraindications to NRT. We intend to enroll 616 participants across 3 sites (MUSC, VA and Yale).

**Sources of Materials.** The sources of data for participants in this project is open-ended questions through interviewer-administered self-report questionnaires of background, behavior (eg, smoking), and cognitions (eg, motivation). Questionnaires will be administered at the time of intake (i.e., the lung cancer screening appointment), and at 1, 3, and 6 months for follow-up. All responses will be collected on a secure, password-

protected, electronic Web-based form. The data will be sent to a secure database in REDCap. Only research staff members have access to the database. The data obtained from VA participants will be housed in the VA REDCap database.

We will collect demographic information, as well as diagnostic medical information related to their screening. Identifiable information will be collected and used to enroll, treat, and contact participants. It will only be used for this purpose.

Research data will be collected using in-person interviews and self-reports. All identifiable information will be stored in a locked file cabinet. All identifiable information collected from VA patients will be stored in a locked cabinet in [name] office room C405 at the Ralph H Johnson VA Hospital. All participants will be assigned a study participant ID made up of numbers and letters. Subsequently, participants will be identified in the Case Report Forms (CRFs) only by that number (e.g., CM24). A list of MUSC IDs and the corresponding names will be maintained by the Principal Investigator and stored on the MUSC BOX.Com site. Digital data with PHI will be stored on a secured server. A list of VA IDs and the corresponding names will be maintained by the site Principal Investigator, [name], and stored on the V drive behind the VA firewall. Digital data without PHI may be stored and analyzed on a laptop or desktop computer.

**Potential Risks.** The risks to participating in these studies are minimal. Participants are informed in advance about the content of the educational materials that they will receive and the kinds of questions that they will be asked. They are also informed that they may terminate participation without penalty. Moreover, they are informed that, if any pre- or post-intervention question seems too personal or if they prefer not to respond for any reason, they can skip the question without penalty. There is also the risk of loss of confidentiality and privacy. Some participants will be offered nicotine replacement therapy (NRT), and there are risks in taking NRT. The NRT used in this study (patch and lozenge) is a standard smoking cessation intervention and is available over-the-counter. The most common adverse effect of nicotine transdermal delivery is topical skin irritation, ranging from mild erythema to a more generalized skin reaction, frequently in subjects with a history of eczematous dermatitis. The most common adverse effects of nicotine replacement lozenges are upset stomach and heartburn.

